## 9.3 VARIABLES

Physician related data about their knowledge and prescribing attitude for systemic thiocolchicoside containing medicinal products and drug utilisation data will be collected.

### 1) Physicians demographics and practice information:

Physician's related data include:

- Demographics (age, gender)
- Duration of practice
- Specialty
- Type of setting

### 2) Screener:

- Prescription of systemic thiocolchicoside containing medicinal products within the last 12 months (yes/no)

### 3) Question to evaluate the physician experience in treating patients presenting with painful muscle contractures:

- Number of prescriptions (not patients) of systemic (oral and/or intramuscular) thiocolchicoside containing medicinal products written within the last 12 months

The following information will also be assessed:

### 4) Prescribing conditions and safety information/warnings of systemic thiocolchicoside containing medicinal products:

- Knowledge of the prescribing conditions and safety information about systemic thiocolchicoside presented in the DHPC and EM:
  - Indication
  - Contraindicated conditions
  - Recommended maximal dose, posology and duration of use for oral and IM forms
  - Information to be communicated to a patient before prescribing the drug
  - Specific information to be advise to females of childbearing potential

### 5) Awareness of and attitude towards the latest prescribing conditions and safety information:

- Awareness of the prescribing conditions and safety information about systemic thiocolchicoside presented in the DHPC and EM:

- Awareness of the prescribing conditions and safety information: main concerns perceived
- Sources of knowledge
- Reception of the DHPC by the physician and awareness about the EM
- Physician's intention to consider the prescribing conditions and safety warnings

6) Recent prescriptions details:

The following information related to up to the last five prescriptions to patients will be collected upon physician's recall memory:

- Approximate date of prescription of systemic thiocolchicoside
- Approximate patient' age at the time of prescription (age ranges: <16 or ≥16 years old)
- Gender
- Status at the visit for females of childbearing potential (using or not an effective method of contraception, pregnant or not, planning to be pregnant, breastfeeding)
- Indication for which the drug was prescribed
- Form, number of administrations and dose per administration per day
- Duration of use prescribed
- Concomitant treatment(s) ongoing or written at the time of prescription
- Main reasons for choosing systemic thiocolchicoside
- Information and recommendations provided to the patient when prescribing systemic thiocolchicoside containing medicinal products.

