## 7.2 RATIONALE

This joint post-authorisation safety study (PASS) survey, requested by PRAC on 8 October 2015, will be conducted in complement to a Joint DUS. Through the prescription details collected, it will also assess the information rarely reported in databases (e.g. pregnancy, lactation and contraception).

This survey is designed to assess the effectiveness of the DHPC and EM, and whether physicians received the updated prescribing conditions and safety warnings/information, understood and follow them when prescribing systemic thiocolchicoside, in four selected European countries (France, Greece, Italy, Portugal).

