### 8.2 OBJECTIVE

The survey objective is to measure the effectiveness of the DHPC and EM, implemented as part of RMMs, by ascertaining the proportion of targeted physicians who understood and implemented the latest prescribing conditions and safety information about systemic thicolchicoside provided in the DHPC and EM.

Specific objectives were to evaluate the proportion of physicians who:

- prescribe systemic thicolchicoside only as adjuvant treatment of painful muscle contractures associated with acute spinal pathology in adults and in adolescents from 16 years onwards.
- do not prescribe systemic thicolchicoside for long-term treatment of chronic conditions.
- follow the recommendations regarding the doses and duration restriction:
  - for oral forms: the recommended and maximal dose is 8 mg every 12 hours, i.e. 16 mg per day. The treatment duration is limited to 7 consecutive days.
  - for IM forms: the recommended and maximal dose is 4 mg every 12 hours, i.e. 8 mg per day. The treatment duration is limited to 5 consecutive days.
- do not prescribe systemic thicolchicoside during pregnancy and lactation.
- do not prescribe systemic thicolchicoside in women of childbearing potential not using adequate contraception.

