### **Sample of collected prescriptions:**

For the data on prescriptions, the statistical unit considered will be the individual drug prescription to patient. Although the level of contribution to this section per interviewed physician is not known and will depend both on the market sells of systemic thicolchicoside in each country and for each specialty, and on the percentage of interviewed physicians who prescribed the drug to patients. Physicians are requested to report up to 5 last prescriptions of systemic thicolchicoside written over the last 12 months before the survey, each pertaining to a unique patient.

As a result, the sampling method (systematic sampling) is expected to allow generalisability of results once the overall sample of physicians can be shown to be generalisable.

Based on IMS Medical Radar experience from previous similar surveys, it is estimated that in average each interviewed physician who prescribed systemic thicolchicoside to patients will contribute with 3 prescriptions on average.

If a conservative rate of 50% is assumed to evaluate the part of interviewed physicians who prescribed systemic thicolchicoside to patients, the sample size for prescriptions will be about 900, thus largely sufficient for the study of proportions of appropriate use of drug under the same assumptions of confidence interval and precision as described above.

Note that a sample adjustment will be also implemented for the sample of collected prescriptions using the same methodology as for analysable questionnaires but with different weights.

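### The objectives on not prescribing in pregnancy, in lactation or without contraception are set per physician, but section 9.3 lists no variable that measures this behaviour per physician

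*Protocol*

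**What the plan says.** Section 8.2 opens its list with "Specific objectives were to evaluate the proportion of physicians who". Among the behaviours listed are that they "do not prescribe systemic thicolchicoside during pregnancy and lactation", and that they do not prescribe "in women of childbearing potential not using adequate contraception". The parent objective concerns physicians who understood and also implemented the conditions.

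Section 7.2 gives the prescription details a specific job. Through them the survey is to complement the drug utilisation study, since "it will also assess the information rarely reported in databases (e.g. pregnancy, lactation and contraception").

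Section 9.3 lists the variables:
- Item 3 asks for the number of prescriptions written in the last 12 months.
- Item 4 covers knowledge.
- Item 5 covers awareness, sources and intention.
- Item 6 covers recent prescriptions: details "related to up to the last five prescriptions to patients will be collected" from recall. They include contraception, pregnancy and breastfeeding status for women of childbearing potential.

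Section 9.5.2 makes the individual prescription the statistical unit for item 6. It assumes that 50% of interviewed physicians will supply prescriptions and that each of these "will contribute with 3 prescriptions on average".

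Section 9.7.1 plans the physician-level proportion as those who received, understood and agreed to apply the conditions. Section 9.7.3 scores physicians on whether their answers are appropriate.

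**The concern.** An objective of the form "do not prescribe systemic thicolchicoside during pregnancy and lactation", expressed as a proportion of physicians, needs a variable that classifies each physician by behaviour. Section 9.3 lists none. Knowing that a use is contraindicated, or intending to respect the warning, is not evidence of having done so. A handful of recalled prescriptions shows what happened to those patients. If all of them were men, they say nothing about these restrictions.

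The report may therefore have to answer a question about physicians' behaviour with answers about knowledge, or with a reading of item 6 that it cannot bear. That second reading errs in one direction: it makes the measures look more effective than they are. The gap has to be closed before fieldwork, because no analysis plan can recover a variable that was not collected.

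**Working it through.** **The plan's own figure.** 600 physicians × 50% × 3 prescriptions = 900, which matches the stated figure of about 900. On the same assumption, 300 of the 600 physicians supply no prescription at all. That sits oddly with the inclusion criterion of having prescribed within 12 months.

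**What each data source can estimate.**
1. Items 4 and 5, scored as in section 9.7.3: the proportion of physicians with appropriate knowledge or intention. This is per physician, but it is not behaviour.
2. Item 6, per prescription: the proportion of reported prescriptions in breach. This is behaviour, but not per physician.
3. Item 6, aggregated per physician: no rule is stated for doing this. The steps below show what would follow if it were done.

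**Average volume.** Annual prescriptions (Table 7.1–1) divided by physicians in the targeted specialties (Table 9.5.2–2):
- France: 3,072,412 / 95,919 = 32.0
- Italy: 1,899,171 / 54,437 = 34.9
- Portugal: 473,337 / 7,014 = 67.5
- Greece: 400,976 / 5,808 = 69.0

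These are rough averages. The numerators include specialties outside the survey (in Italy, GPs and orthopedists together account for 71.9% + 20.5% = 92.4%). The denominators include non-prescribers and, outside France, omit rheumatologists, whose counts are not available.

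**Probability that a breach goes unseen.** Suppose a physician writes N prescriptions a year, b of them in breach and spread evenly, and reports the last k. The chance that none of the k is a breach is C(N−b, k) / C(N, k). For b = 1 this is 1 − k/N. The protocol gives no breach rate, so b is an assumption and is varied.

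| N | b | k = 3 | k = 5 |
|---|---|---|---|
| 32 | 1 | 29/32 = 91% | 27/32 = 84% |
| 69 | 1 | 66/69 = 96% | 64/69 = 93% |
| 32 | 3 | 74% | 59% |
| 69 | 3 | 87% | 80% |
| 32 | 5 | 59% | 40% |
| 10 | 1 | 70% | 50% |
| 5 | 1 | 40% | 0% |

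**Where most breaching physicians stop being missed.** Detection reaches one half when 1 − (1−p)^k = 0.5, where p is the share of a physician's prescriptions in breach. This gives p of about 21% for k = 3 and 13% for k = 5. With a single breach in the year, the share missed falls to half at N = 6 (k = 3) or N = 10 (k = 5).

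**Effect on a physician-level proportion.** Take N = 32 and an assumed 2% of prescriptions in breach. Physicians with no breach in the year: 0.98^32 = 52%. Physicians with none among those reported: 0.98^3 = 94% or 0.98^5 = 90%.

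**The case against.** The strongest reply is that the protocol never says a physician is judged from the last few prescriptions. Section 9.5.2 makes the prescription the unit, and sections 9.7.1 and 9.7.3 take the physician-level proportion from questionnaire answers. That is correct. A reader might infer that the survey will count a physician with no breach among three to five prescriptions as compliant, and so report close to 100% whatever the real practice. The documents plan no such analysis.

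Nor is a per-prescription proportion biased merely because few are taken from each physician. If 2% of prescriptions were in breach, about 0.02 × 900 = 18 would be expected to show it. It would therefore be too strong to say that the survey cannot supply the information promised in section 7.2.

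Three further points stand:
- The objective names no 12-month window. That window comes from the eligibility criterion and the prescription look-back.
- The percentages missed depend on breach frequency and volume, so they are not general.
- The questionnaire is a stand-alone document listed in Annex 1 and is not shown. One can say only that section 9.3 lists no such variable.

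Section 9.9.4 already admits recall and selection bias for item 6 and calls for caution. It does not say that these data cannot show a physician refrains from prescribing to these groups. None of these replies supplies a measure of the quantity stated in section 8.2.

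**Conclusion.** The point holds as a mismatch between objective and data. The behavioural objectives on pregnancy, lactation and contraception are proportions of physicians. The behavioural data are per prescription, the physician-level data are knowledge and intention, and no stated rule connects them.

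The percentages in the working measure the danger of one particular reading, not an error in a planned analysis. At average volumes of about 32 to 69 prescriptions a year, with one evenly spread breach, that reading would miss 91–96% of breaching physicians at three prescriptions and 84–93% at five. It would miss half or fewer of them when breaches are frequent or volume is low. Confidence is medium, because the breach rate, the spread of volume between physicians and the questionnaire items are all unknown.

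**What to change.** Either change closes the gap, and both can be made.

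1. **Restate the objective.** In section 8.2, and where it is repeated in the synopsis and section 4.3, word the behavioural part as the proportion of reported prescriptions in breach. For the pregnancy, lactation and contraception items, use prescriptions to women of childbearing potential as the denominator; item 6 already collects their status. State in sections 9.7 and 9.9.4 that these data do not establish that a physician does not prescribe in these groups. The cost is wording only. The denominator will be smaller than 900, by a share that the protocol does not give, so precision for these items should be stated separately.

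2. **If the physician-level objective is kept, measure it.** Add a closed item for each situation, asking about any such prescribing in the last 12 months: never, once, more than once, do not know. Report the answers as self-reported behaviour. The cost is a few closed items, about a minute on a 10 to 15 minute core questionnaire. The drawback is the social desirability that section 9.9.3 already recognises, which also pushes towards apparent compliance; its size is unknown.

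If the questionnaire already contains such items, list them in section 9.3 and link each to its objective.

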## **9.6 DATA MANAGEMENT**

The survey will be conducted according to the Standard Operating Procedures (SOPs) of IMS Medical Radar and IMS Real World Evidence Solutions.

Collected data will be entered and stored in a database specific to the survey and the country. A study database will be created by merging of databases of each country.

Data will be checked in terms of consistency before data analysis:

- removal of duplicates (if required),
- data labelling and data formatting,
- range and consistency checks for each variable to identify potential non admissible values,
- cross-check the consistency of data for related variables (if feasible).

The number of variables with missing values will be indicated. Missing values are excluded from the calculation of percentages.  
The study database will be locked once validated.

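### Patient age is recorded only as under 16 or 16 and over, so the prescription-level contraception result has no denominator independent of the physician being assessed

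*Protocol*

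**What the plan says.** Protocol section 9.3 item 6 lists what is collected for up to five recent prescriptions per physician. Age is defined as "Approximate patient' age at the time of prescription (age ranges: <16 or ≥16 years old", and gender follows. The next item is "Status at the visit for females of childbearing potential (using or not an effective method of contraception, pregnant or not, planning to be pregnant, breastfeeding". No age range, definition or rule says which female patients fall under it. All of these details "will be collected upon physician's recall memory", and section 9.9.4 explains that no patient records are consulted.

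These data have a stated purpose. Section 7.2 says of the prescription details that "it will also assess the information rarely reported in databases (e.g. pregnancy, lactation and contraception". Section 8.2 has as a specific objective the proportion of physicians who "do not prescribe systemic thicolchicoside in women of childbearing potential not using adequate contraception", and the research question in section 8.1 singles out pregnancy, lactation and contraception.

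**The concern.** The two age ranges serve the under-16 restriction. They do not serve the contraception objective, because a woman of 25 and a woman of 75 get the same age code. To judge how often the contraception restriction was followed, one needs a denominator of women to whom it applied. Here that denominator exists only through the answer of the physician whose prescribing is being assessed.

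A physician who did not think about childbearing potential at the visit may not place the woman in that group when recalling the case. Nothing else in the record would show her to be of reproductive age. If such women are more often without contraception than those who were considered, the reported result is too favourable. Anonymous recall without chart review leaves no way to rebuild the denominator later.

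**Working it through.** **1. What the recorded fields can form.** Age range and gender give four cells, and the only relevant one is females aged 16 or over. The subset of childbearing potential comes only from the physician's use of the status item. The consistency checks in section 9.6 and the real-time checks in section 9.8.2 cannot flag a woman of 30 with no status, because her age is not held.

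**2. The plan's own figure.** Section 9.5.2 expects about 900 prescriptions. This reproduces: 600 physicians × 50% contributing × 3 prescriptions each = 900. The documents do not say how many of these go to women of childbearing potential, so everything below uses assumed shares.

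**3. Direction and possible size.** Let t be the true share without contraception among women of childbearing potential, m the fraction of those women whom physicians leave out of the group, and k the fraction left out among the rest.

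Reported share = t(1 − m) / [t(1 − m) + (1 − t)(1 − k)]

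If m = k, the reported share equals t and there is no bias. If m exceeds k, the reported share is too low. With k = 0:

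| True t | m = 25% | m = 50% | m = 75% |
|---|---|---|---|
| 10% | 7.7% | 5.3% | 2.7% |
| 20% | 15.8% | 11.1% | 5.9% |
| 30% | 24.3% | 17.6% | 9.7% |

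For example, with t = 20% and m = 50%: 0.10 / (0.10 + 0.80) = 11.1%.

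**4. The fallback denominator.** Using all females aged 16 or over does not solve it. If a fraction f of them is of childbearing potential, a true 20% appears as 0.20 × f, which is 6%, 10% or 14% for f = 30%, 50% or 70% (assumed).

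**5. What a preset age band would add.** Assume that half of the 900 prescriptions go to women and that 40% of those women are in the reproductive-age band: 900 × 0.5 × 0.4 = 180.

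- Suppose 108 use contraception, 18 do not and 54 have unknown status. Among known status, use is 108/126 = 85.7%. Counting the unknowns each way gives 108/180 = 60.0% and (108 + 54)/180 = 90.0%.
- With 18 unknown and 139 of the other 162 using contraception, it is 139/162 = 85.8%, with bounds 139/180 = 77.2% and 157/180 = 87.2%.

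The known-status figure is almost the same in both cases, while the bounds differ widely. Under section 9.3 as written, a reader could not tell the two situations apart, because there is no count of reproductive-age women with no recorded status.

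**The case against.** The strongest reply is that section 9.3 is a list of variables. The questionnaire is a separate document (Annex 1) and is not shown. It may ask about childbearing potential directly, force an answer or offer a don't-know option. That stands. A reader might infer that the status item has no such option, that physicians will leave it blank, and that the section 9.6 rule "Missing values are excluded from the calculation of percentages" then drops the case. The documents do not show this. The bracket after the status item summarises content and need not be the answer list. A woman classed as not of childbearing potential would be not applicable, which is different from missing. It does not answer the point, however: any such question would still be the assessed physician's own classification, and the protocol itself fixes age at two ranges.

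It is also fair that childbearing potential is a clinical judgement and no age band captures it exactly, that the physician can still flag these women, and that section 9.9.4 already admits recall and selection bias in this part of the survey and promises cautious interpretation. That admission concerns which cases are recalled and reported. It does not cover who is counted in the denominator among the cases that are reported.

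Finally, the reach is limited. Prescriptions to women known to be pregnant or breastfeeding can be counted over all females aged 16 or over. The knowledge questions in section 9.3 item 4 do not use this denominator. The information given to each patient is collected as a second signal.

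**Conclusion.** The point holds for the prescription-level contraception result. Its denominator is set from memory by the physician being assessed, and the recorded age gives no independent check on it. The result is biased toward compliance if the women left out are more often without contraception than those included. That is plausible, but it is an assumption, and the documents give no figure from which to estimate the amount. With equal omission in both groups there is no bias.

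A reader might set 86% against 60% in the illustration and take the gap as the bias. That is not supported. The shares are assumed, and the two figures measure different things: use among women with known status, and confirmed use among all women in the band. The 60% is a lower bound, and the matching upper bound is 90%. Nor do the documents support extending the point with the same force to the pregnancy and lactation counts.

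The change is worth making before the questionnaire is fielded, because it is nearly free and the information cannot be obtained afterwards.

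**What to change.** In section 9.3 item 6:

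- Split the upper age range, for example into 16–50 and over 50 years, or record approximate age in years. The cut-off is an analysis convention only.
- Ask the status item for every female in the reproductive-age band, and make sure the answers include one for not of childbearing potential and one for not asked or not known.
- Report contraception, pregnancy and lactation status over all females in that band, with not asked or not known as its own category.
- Give the contraception proportion among women with known status, and again with the unknowns counted each way as bounds. Do not score unknown status as non-compliance: for prescriptions up to 12 months old, not asked at the visit is hard to separate from not remembered now.

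The cost is one age category and one or two answer options. The band only approximates childbearing potential, and age and status would still be recalled by the physician, so recall bias remains. The gain is a preset denominator and a count of women with no known status.
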